9.4.3 ANALYSIS OF THE SECONDARY ENDPOINT

In order to maintain the overall type I error at the 0.05 level, an hierarchy will be employed as follows: If the primary endpoint is found to be significant at a significance level of 0.05, then the first key secondary endpoint will be tested; if this endpoint is found to be significant in a significance level of 0.05, then the second key secondary endpoint will be tested and so on. The key secondary endpoints and their order in the hierarchy are:

UMSARS sub-scores: The secondary outcome endpoint (UMSARS-1 and UMSARS-2 scores) will be analyzed by comparing the mean decline in total UMSARS-1 and UMSARS-2 score in the active sirolimus group (UMSARS-1 and UMSARS-2 at week 48 minus UMSARS-1 and UMSARS-2 at baseline) with the pre-specified fixed value of 4.5 (SD: 5.5) in each score using a one-sample t-test.

Brain magnetic resonance imaging: The secondary outcome endpoint (putaminal diffusivity) will be analyzed by comparing the mean increase in Trace(D) score in the active sirolimus group (Trace(D) score at week 48 minus Trace(D) score at baseline) with the pre-specified fixed value of 0.07 ($\times 10^{-3}$ mm²/sec) using a one-sample t-test.

Retinal optical coherence tomography: The secondary outcome endpoint (retinal nerve fiber layer

thickness) will be analyzed by comparing the mean decline in RNFL thickness in the active sirolimus group (RNFL at baseline minus RNFL at week 48) with the pre-specified fixed value of 3.7 μm using a one-sample t-test.

Concentration of exosomal αSyn particles: This exploratory outcome endpoint will be analyzed by comparing the mean change in αSyn exosomal particles concentration (week 48 minus baseline) in the active sirolimus group with the placebo group.

In all cases missing data will be addressed by using a regression-based multiple imputation model (78)

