4 STUDY DESIGN

4.1 OVERALL DESIGN

To determine whether to test sirolimus in a large phase 3 trial, we propose to conduct a clinical trial of sirolimus in MSA using a futility design. A futility design under the null hypothesis assumes that sirolimus will slow the progression of the disease, whereas the alternative hypothesis assumes no benefit of sirolimus. If the null hypothesis is rejected (i.e., futility of sirolimus to slow progression of MSA), major phase 3 studies will be discouraged, whereas non-futility will offer strong support for a phase III trial to detect clinical efficacy.

To test this hypothesis we will perform a single-center, randomized, double blind, placebo-controlled, phase-II, futility trial, chosen as an efficient approach to determine if sirolimus would be worthy of future investigation in larger, more definite trials. This trial was designed to compare the mean value for the primary outcome measure, change in total Unified Multiple System Atrophy Rating Scale (UMSARS) score from baseline to week 48, between the sirolimus arm and a pre-specified fixed value, representing a 4-point reducing in the expected mean decline without treatment; this fixed value was obtained using data from previously completed a large natural history study(39) and the placebo arm of a recently completed clinical trial in MSA (40). The 4-point reduction was based on the recently reported minimally clinically important decline (MICD) in the total UMSARS score of 3.5-points (38).

The null hypothesis is that sirolimus will reduce the mean decline in the total UMSARS score over 12 month by, at least 4-points, compared with the expected (fixed) value obtained from the historical controls. If the null hypothesis is rejected, then the drug would be considered futile for further investigation in MSA. If the null hypothesis is not rejected, sirolimus would be considered for a phase 3 clinical trial.

Thus, the primary goal is to evaluate the effect of sirolimus on progression of MSA, including autonomic, cerebellar and parkinsonian features as measured by the UMSARS, a relevant clinical measure of disease progression. Secondary goals are to determine if there is any effect on neuroimaging (brain MRI) and ophthalmological (retinal OCT) biomarkers of the disease. As exploratory aim we will determine if there are any changes in plasma α Syn exosomes, as surrogate markers of autophagy.

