4.2 SCIENTIFIC RATIONALE FOR STUDY DESIGN

To determine whether to test sirolimus in a large phase 3 trial, we propose to conduct a clinical trial of sirolimus in MSA using a futility design. This approach minimizes the number of subjects and resources required for the study and provides an indication of whether or not to pursue larger and more definite studies. A futility design (60) is highly appropriate for MSA given: a) the low prevalence of the disease; b) the availability of historical controls from recent large studies (8, 39); and c) the availability of sensitive outcome measures. A futility design under the null hypothesis assumes that sirolimus will slow the progression of the disease, whereas the alternative hypothesis assumes no benefit of sirolimus. If the null hypothesis is rejected (i.e., futility of sirolimus to slow progression of MSA), a major phase III study will be discouraged, whereas non-futility will offer strong support for a phase III trial to detect clinical efficacy.

This study will also include a placebo group in 3:1 proportion. Our reason for including a placebo arm is to facilitate blinding to treatment assignment and also to permit a descriptive assessment of the validity of the assumed change in UMSARS over time in the historical control group; it will not be used as a basis of comparison for the active treatment arm.

This placebo-controlled futility design comparing outcome measures to historical controls has been used in other neurodegenerative disorders (61-63).

The study population (n=42 active agent, n=14 placebo) was selected based on power analysis calculation using the known annual progression of the UMSARS total score from published natural history studies (8, 39) and the progression in the placebo group of previous clinical trials of MSA(40), as well as from the minimally clinically significant difference in UMSARS (38) (see statistical section).

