9 STATISTICAL CONSIDERATIONS

9.1 STATISTICAL HYPOTHESES

Primary Efficacy Endpoint: We hypothesize that treatment with sirolimus will show promise to slow the progression of the disease of patients with MSA. Specifically, our null hypothesis is that patients receiving sirolimus will have a UMSARS total score progression of only 4.6 points at week 48 higher than baseline, compared to a progression of 8.6 points at week 48 from baseline reported in historical controls from natural history studies and placebo-controlled trials of MSA. Our alternate hypothesis is that sirolimus will be futile to slow the progression of the disease in patients with MSA. The statistical definitions are as follows:

$H_0: \theta_E - \theta_p \leq 4$ where $\theta_p = 8.6$ points increase at week 48 from baseline described in historical controls
 $H_0: \theta_E \leq 4.6$ points increase at week 48 from baseline
 $H_1: \theta_E > 4.6$ points increase at week 48 from baseline

Secondary Efficacy Endpoints:

Brain MRI: We hypothesize that treatment with sirolimus will slow the increase of putaminal diffusivity in patients with MSA. Specifically, our null hypothesis states that patients receiving sirolimus will have a putaminal Trace (D) total score progression of 0.030×10^{-3} mm²/sec or less at week 48 versus baseline, compared to a progression of 0.070×10^{-3} mm²/sec at week 48 from baseline reported in specific longitudinal studies of MSA (41).

$H_0: \theta_E - \theta_p \leq 0.04$ where $\theta_p = 0.07$ ($\times 10^{-3}$ mm²/sec) increase in putaminal diffusivity at week 48 from baseline described in specific studies
 $H_0: \theta_E \leq 0.03$ points increase at week 48 from baseline
 $H_1: \theta_E > 0.03$ points increase at week 48 from baseline

Optical coherence tomography: We hypothesize that treatment with sirolimus will slow the thinning of the retinal nerve fiber layer (RNFL) in patients with MSA. Specifically, our null hypothesis states that patients receiving sirolimus will have a RNFL thickness thinning of 1.45 μ m at week 48 versus baseline, compared to a decrease of 3.7 μ m at week 48 from baseline reported in specific longitudinal studies of MSA (12).

$H_0: \theta_E - \theta_p \leq 2.25$ where $\theta_p = 3.7$ μ m decrease in RNFL at week 48 from baseline described in specific studies
 $H_0: \theta_E \leq 1.45$ μ m decrease at week 48 from baseline
 $H_1: \theta_E > 1.45$ μ m decrease at week 48 from baseline

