9.4.2 ANALYSIS OF THE PRIMARY EFFICACY ENDPOINT

The primary outcome endpoint (UMSARS total score) will be analyzed by comparing the mean decline in total UMSARS score in the active sirolimus group (UMSARS total score at week 48 minus UMSARS total score at baseline) with the pre-specified fixed value of 8.6 (SD: 9.2) using a one-sample t-test. If the difference between the fixed value of 8.6 minus the UMSARS total score in the active sirolimus group is 4 or less, the null hypothesis will be rejected, indicating futility.

Missing data will be addressed by using a regression-based multiple imputation model (78)

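### Section 9.4.3 opens the secondary tests only when the primary is significant, which in this design means futile, and it tests MRI and OCT against untreated values rather than the null thresholds of 9.1

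*Combined protocol and SAP*

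**What the plan says.** **Primary.** Section 9.1 takes as null that the mean UMSARS total increase on sirolimus is at most 4.6 points (8.6 untreated minus 4) and as alternative that it exceeds 4.6. Section 4.1 gives the consequence: "If the null hypothesis is rejected, then the drug would be considered futile for further investigation in MSA". Section 9.4.2 compares the sirolimus mean "with the pre-specified fixed value of 8.6 (SD: 9.2) using a one-sample t-test", then adds a margin rule: when the difference formed by 8.6 minus "the UMSARS total score in the active sirolimus group is 4 or less, the null hypothesis will be rejected, indicating futility".

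**Gate.** Section 9.4.3, with the stated aim of holding overall type I error at 0.05, says: "If the primary endpoint is found to be significant at a significance level of 0.05, then the first key secondary endpoint will be tested". The later endpoints follow in the same way.

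**Secondary comparisons.**
- MRI: in 9.1 the null is an increase of at most 0.03 (×10⁻³ mm²/sec), against 0.07 untreated. In 9.4.3 the test uses "Trace(D) score at week 48 minus Trace(D) score at baseline) with the pre-specified fixed value of 0.07".
- OCT: in 9.1, "our null hypothesis states that patients receiving sirolimus will have a RNFL thickness thinning of 1.45" µm, against 3.7 untreated. In 9.4.3 the test value is 3.7.
- UMSARS-1 and UMSARS-2: 9.1 states no null. Section 9.4.3 compares each "with the pre-specified fixed value of 4.5 (SD: 5.5) in each score using a one-sample t-test". The assumed benefit is 2 points in the synopsis (1.1) and 2.5 points in section 3.

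On a favourable outcome, section 4.2 says "non-futility will offer strong support for a phase III trial to detect clinical efficacy".

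**The concern.** A gate that needs a significant primary is standard in an efficacy trial, where significance means benefit. Here the null is that the drug is promising, so significance means futility. In the one case the protocol treats as support for phase III, the plan allows no formal test of UMSARS-1, UMSARS-2, MRI or OCT.

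If the gate does open, the tests that follow ask a different question from the primary. Rejecting against 0.07, 3.7 or 4.5 in the hoped-for direction shows benefit over untreated progression. One hierarchy would then join a conclusion of futility to conclusions of benefit, and its type I error statement would have no clear meaning.

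Without a correction, the analyst has to choose the meaning of *significant*, the direction and the threshold, possibly after seeing the data.

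**Working it through.** **Inputs.** Untreated mean 8.6, SD 9.2, target benefit 4, one-sided alpha 0.05, power 0.80 and 38 evaluable sirolimus patients, 42 with dropout (9.2). Sub-score reference 4.5, SD 5.5 (9.4.3). Sub-score benefit 2 (1.1) or 2.5 (section 3). MRI and OCT thresholds from 9.1. Powers use the noncentral t distribution.

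**The plan's own figures.** The pooled mean reproduces: (96 × 7.5 + 50 × 10.8)/146 = 8.63. The 38 does not: (9.2 × (1.645 + 0.842)/4)² = 32.7, so 33 by the normal formula and 35 by the t-test. At n = 38 the one-sided power is 83.8%. The difference is on the safe side and does not bear on this point, so I keep 38.

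**Thresholds side by side.**

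| Endpoint | Untreated (tested in 9.4.3) | Null threshold | Gap |
|---|---|---|---|
| MRI | 0.07 | 0.03 (9.1) | 0.04 |
| OCT | 3.7 | 1.45 (9.1) | 2.25 |
| UMSARS-1, UMSARS-2 | 4.5 | not stated; implied 2.5 or 2.0 | 2 or 2.5 |

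For MRI and OCT the gap is the whole assumed effect. Section 9.4.3 has no margin rule like the one in 9.4.2 to bridge it.

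**How often the gate opens.** SE = 9.2/√38 = 1.492. The one-sided critical mean against 4.6 is 4.6 + 1.687 × 1.492 = 7.12.

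| Reading of *significant* (n = 38) | Drug at target (mean 4.6) | Useless drug (mean 8.6) |
|---|---|---|
| One-sided 5% test against 4.6 (9.1, 9.2) | 5% | 84% |
| Literal point rule of 9.4.2 (observed mean 4.6 or more) | 50% | 99.6% |
| Two-sided 5% test against 8.6 | 74% | 5% |
| One-sided 5% test against 8.6, benefit direction | 84% | 5% |

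The point rule carries no significance level. It is listed because it is the literal futility rule in 9.4.2. With n = 42 the first three rows become 5%/87%, 50%/99.8% and 79%/5%.

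**What a sub-score test shows once open.** SE = 5.5/√38 = 0.892, with a 2-point benefit.
- Against 4.5: at target it rejects 71% of the time one-sided in the benefit direction and 59% two-sided. For a useless drug it rejects 5%.
- Against 2.5, as a one-sided futility test: it rejects 5% at target and 71% for a useless drug.

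The same endpoint thus gives opposite messages depending on the comparison value.

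**The two steps combined.** Suppose the primary must be futile (one-sided against 4.6) and a sub-score then beneficial (one-sided against 4.5). Assuming normal data and equal sub-score SDs of 5.5, a total SD of 9.2 implies a correlation of 9.2²/(2 × 5.5²) − 1 = 0.40 between sub-scores, and 5.5 × 1.40/9.2 = 0.84 between total and sub-score. Simulating 100,000 trials per scenario, both steps pass in 0.9, 1.3, 1.2, 0.7 and 0.3% of trials at 0, 25, 50, 75 and 100% of the target benefit.

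**The case against.** Three arguments on the other side deserve weight.

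1. *Significant* may have meant better than 8.6, since 9.4.2 names a t-test against 8.6. That would make the gate sensible and the secondary tests consistent with it. No section says so, however, and it conflicts with the hypotheses in 9.1, with the fixed value in 9.2 that already includes the 4-point reduction, and with the futility conclusion in 9.4.2. The MRI and OCT nulls in 9.1 would still not match their tests.

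2. In a futility design the type I error is false futility. A fixed sequence of futility nulls would control it, and 9.1 might be taken to supply the MRI and OCT margins while 9.4.3 only names the reference values, much as 9.4.2 does for the primary. This is the stronger reading. But 9.4.2 writes its margin rule out and 9.4.3 does not, UMSARS-1 and UMSARS-2 have no null in 9.1 to draw on, and a non-futile result would still leave every secondary untested.

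3. The consequence is limited. Estimates can be reported whatever the gate does, and the imaging aims are only to assess potential effects. That is true and it bounds the severity. The combined pass rates also describe a success criterion that the plan never states, so they illustrate the incoherence and are not operating characteristics the sponsor intended.

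**Conclusion.** The concern holds. As written, the secondary hierarchy opens on futility, and the MRI and OCT tests are not tests of the hypotheses in 9.1. Under the 9.1 reading, a drug that meets its target gets formal secondary tests in 5% of trials and a useless one in 84% (n = 38, SD 9.2, normal data). The alternative reading reverses the order to 74% and 5%, so one undefined word decides which drug is tested further.

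The mismatch in comparison values rests on the text alone. The documents give no SD for MRI or OCT, so no power is quoted for those endpoints. The exploratory exosome comparison lies outside this point. The defect should be fixed, but it does not touch the primary go/no-go decision.

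**What to change.** By protocol amendment:

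1. Remove the condition on a significant primary from 9.4.3 and analyse every secondary endpoint whatever the primary result.
2. Report each mean change with a 95% confidence interval, set against both the untreated value (4.5, 0.07, 3.7) and the target threshold, as supportive evidence with no family-wise claim. For a sub-score the half-width is about 2.026 × 0.892 = 1.81. An observed mean of 2.5 gives 0.7 to 4.3, which excludes 4.5. An observed mean of 4.5 gives 2.7 to 6.3, which excludes 2.5. One interval therefore answers both questions.
3. Where a futility test is kept, make it one-sided against 0.03 (MRI), 1.45 (OCT) and one agreed sub-score threshold. That threshold is 2.5 or 2.0, depending on how the 2-point benefit in 1.1 and the 2.5-point benefit in section 3 are reconciled. State the sub-score null in 9.1. When doing so, note that two references of 4.5 sum to 9.0, not 8.6.

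The cost is wording changes in 1.1, 3 and 9.4.3, plus 9.1 if a sub-score null is added, with IRB approval. It needs no added patients, visits or data. The sponsor gives up the claim of overall type I error control across the secondaries, which the present gate does not deliver in any interpretable form.

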9.4.4 SAFETY AND TOLERABILITY ANALYSES

Adverse events: The incidence and frequency of adverse events will be presented by System Organ Class and preferred terminology according to NCI and CTCAE reporting standard. Aes will also be presented by System Organ Class, High Level Term and preferred terminology. Data will be tabulated by treatment group, sex, age, maximal severity, maximal outcome, maximal action taken and maximal relationship to the tested drug. Serious adverse events and seriousness criteria will be listed and discussed on a case by case basis.

Laboratory tests: The incidence of laboratory tests outside the normal range and the incidence of measurements of potential clinical significance will be presented by treatment group. Shift analysis of these counts from baseline will also be provided. Descriptive statistics as well as their changes from baseline will also be presented by study group.

Vital Signs & Height/Weight: Incidence of measurements of potential clinical significance will be presented by study group. Shift analysis from baseline will be provided as well. Descriptive statistics of vital signs & height/weight, as well as, their changes from baseline, will be presented by study group.

EKG: The incidence of abnormal measurements will be presented by treatment group. Shift analysis from baseline will be provided as well. Descriptive statistics, as well as, their changes from baseline, will also be presented by study group.

Tolerability assessments: Tolerability analysis will be based on the number (%) of participants who failed to complete the study, the number (%) of participants who failed to complete the study due to adverse events. Time to withdrawal will be presented by Kaplan-Meier curves. Significance testing of time to withdrawal will be done using Cox's proportional hazards model.

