- If sirolimus levels are < 5 ng/mL, the participant will be instructed to take sirolimus 2 mg two capsules daily (4 mg total dose) or matching placebo; sirolimus levels will be then measured again 7 days after the patient began taking 4 mg/day (+ 3 days). If sirolimus levels are between 5 and 20 ng/ml, the subject will continue with that dose until the next measurement of sirolimus levels on Visit (+ 3 days).
- If sirolimus levels are > 30 ng/ml with one capsule/day, the subject will be excluded from the trial due to the high risk of adverse events.

Subjects who were instructed to increase their dose to 4 mg will undergo another measurement of sirolimus levels 7 days after the previous dose adjustment (+ 3 days):

- If sirolimus levels are < 5 ng/mL, the participant will be instructed to increase sirolimus to 2 mg three capsules daily (6 mg total dose) or matching placebo. Sirolimus levels will be then measured 7 days after the patient began taking 6 mg/day (+ 3 days).
- If sirolimus levels are between 5 and 20 ng/ml, the subject will continue with that dose until the next measurement of sirolimus. If the sirolimus levels are > 20 ng/ml, the subject will be instructed to go back to the 2 mg/day dose and continue with that dose until the next measurement of sirolimus levels.

From Visit 3 to Visit 6, sirolimus level blood draw will take place 7 days (+3 days) after the previous dose adjustment has taken place (i.e., 7 days after the patient started taking the adjusted dose).

From Visit 7 onwards, subjects will be instructed to increase or decrease their sirolimus dose (between a min dose of 2 mg/day to a max dose of 6 mg/day) depending on blood levels (target: 5-20 ng/ml) and the emergence of adverse events.

Expected dose-limiting effects requiring sirolimus dose reduction are:

- Grade 2 stomatitis or mucositis
- Grade 2 lymphedema
- Grade 2 proteinuria
- Grade 2 renal failure
- Grade 3 pneumonitis
- Grade 2 diarrhea

Every attempt will be made to maintain the participant on the full dose. If the participant is unable to maintain the full dose, the minimum acceptable dose is 2 mg once a day. An attempt will be made to increase the dose with a re-challenge at a later date. Capsules should be swallowed whole with a glass of water or may be taken with food to minimize gastrointestinal side effects.

To maintain investigator and subject blinding during the clinical trial, the results of the sirolimus

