9.2 SAMPLE SIZE DETERMINATION

This study is a randomized, double blind placebo-controlled futility trial in which the primary outcome measure value (UMSARS total score) in a cohort of patients with MSA taking active agent will be compared to a known value from historical controls previously published in the literature. The primary outcome measure was used to calculate the sample size.

The primary statistical analysis will involve a comparison of the mean absolute difference in the active sirolimus group with a pre-specified fixed value, constituting a 4-point reduction in the expected mean increase in the UMSARS total score over 48 weeks without treatment. The expected mean increase in total UMSARS outcomes were obtained from the *U.S. Natural History Study of MSA* (n=96) (39), that reported that the total UMSARS score at 12 months increased a mean of 7.5 (SD: 8.4) absolute points from baseline. Also data from a phase III double-blind placebo-controlled 12-month clinical trial with rifampicin in MSA performed in the U.S. (40) (which was found to be ineffective to slow the progression of the disease) showed that in patients taking placebo (n=50) the total UMSARS score at 12 months increased a mean of 10.8 (SD: 10.7) absolute points from baseline. A weighted analysis of these two populations showed the pooled total UMSARS score at 12-months in patients with MSA in large studies performed in the U.S. had increased a mean of 8.6 (SD: 9.2) points from baseline.

Also, recent studies (38) have determined that the minimally clinically important difference (MCID) in the total UMSARS score is 3.5 points after 48-weeks from baseline.

Taking into consideration this MCID, for this trial, we will assume a promising difference in the UMSARS total score of 4 points between those taking active agent and the historical controls. Specifically, our null hypothesis is that patients receiving sirolimus will have a UMSARS total score progression of only 4.6 points at week 48 higher than baseline, compared to a progression of 8.6 points at week 48 from baseline reported in historical controls from natural history studies and placebo-controlled trials of MSA. Our alternate hypothesis is that sirolimus will be futile to slow the progression of the disease in patients with MSA. The statistical definitions are as follows:

$H_0: \theta_E - \theta_p \leq 4$ where $\theta_p = 8.6$ points increase at week 48 from baseline described in historical controls

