$H_0: \theta_E \leq 4.6$ points increase at week 48 from baseline

$H_1: \theta_E > 4.6$ points increase at week 48 from baseline

Therefore, assuming an alpha of 0.05, and a power of 0.8 (one sided, as patients with MSA have not been reported to improve spontaneously) to detect a progression of 4.6 points (i.e., 8.6 minus 4) in the UMSARS total score after 48-weeks from baseline we will need to enroll 38 patients in the active agent arm. Anticipating a 10% for dropouts rate, we will need to enroll 42 patients in the active agent arm.

This trial will include a placebo group to facilitate blinding in a 3:1 proportion. However, statistical comparisons for the primary and secondary efficacy outcome measures will be performed between the active agent arm and the historical controls. We will therefore enroll 14 patients in the placebo arm.

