9.3 POPULATIONS FOR ANALYSES

Analyses will be performed according to the intention-to-treat principle and will include all randomized subjects who have completed, at least, 3 months of study drug.

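### No safety population is defined, and the plan's only defined analysis set, read as written, leaves everyone who stops in the first 3 months out of the safety and tolerability results

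*Combined protocol and SAP*

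**What the plan says.** Section 9.3, which covers populations for analyses, contains one rule. It invokes the intention-to-treat principle and then says that analyses "will include all randomized subjects who have completed, at least, 3 months of study drug". Nothing confines this to efficacy.

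Section 9.4.4 covers adverse events, laboratory tests, vital signs, EKG and tolerability. For tolerability it plans counts of participants who do not complete the study, overall and because of adverse events, and then: "Time to withdrawal will be presented by Kaplan-Meier curves. Significance testing of time to withdrawal will be done using" Cox's proportional hazards model. It gives no population, denominator or time origin for any of these.

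Three other sections bear on the point:

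- Section 8.2 makes the number and percentage leaving the study because of an adverse event the primary safety outcome. It requires adverse events to be recorded from consent through 12 months, including after an early stop of study drug.
- Section 6.4 mentions intention-to-treat, complete and per-protocol sets. It refers to sections 12.3.1 and 12.3.2 for the first two, and the document has no section 12.
- Section 6.1.2 places the initial dose selection in the first month and includes this removal rule: "If sirolimus levels are > 30 ng/ml with one capsule/day, the subject will be excluded from the trial".

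**The concern.** A 3-month minimum on drug is a condition on tolerating the drug. If it governs the safety analyses, the people who tolerated it least are removed from the results meant to describe tolerability. The first 3 months include the initial dose selection and the removal of participants with a high level on the starting dose.

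Three outputs would be affected. The adverse-event and laboratory tables would omit early stoppers. The primary safety outcome would omit early discontinuations from its numerator, and those participants from its denominator. The Kaplan-Meier curve would stay at 100% to month 3 by construction, because nobody in the set could have left before then.

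Non-futility is meant to support a phase III trial (4.1), and readers will judge tolerability from these results. The data for early stoppers would have been collected, but no analysis rule clearly uses them.

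**Working it through.** **Inputs.** Section 9.2: 42 participants on sirolimus and 14 on placebo, "Anticipating a 10% for dropouts rate". Section 4.1: 48 weeks of treatment, with month 3 at Day 84, that is, week 12. The 10% is stated for the active arm only. Applying it to both arms, and taking a constant hazard, are assumptions made here.

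**The plan's own figures.** 38 × 1.10 = 41.8, which rounds up to the stated 42 (38/0.90 = 42.2 would give 43). 42/3 = 14. The figure of 38 itself is not reproduced: ((1.645 + 0.842) × 9.2/4)² = 32.7, so 33, or 35 with the t distribution. That is a separate matter; this point uses only 42, 14 and 10%. The plan states no expected number of withdrawals.

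**Expected withdrawals over 48 weeks.** 42 × 0.10 = 4.2 on sirolimus and 14 × 0.10 = 1.4 on placebo, 5.6 in all.

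**Share lost under the 3-month rule.** With constant hazard, the probability of withdrawing by week 12 is 1 − 0.9^(12/48) = 1 − 0.9740 = 0.0260.

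- Lost: 56 × 0.0260 = 1.46 of 5.6, or 26%.
- Left: 56 × (0.9740 − 0.9000) = 4.14.

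**Sensitivity to the rate** (assumed rates, both arms):

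- 20%: 56 × (1 − 0.8^0.25) = 3.0 of 11.2 lost (27%).
- 30%: 56 × (1 − 0.7^0.25) = 4.8 of 16.8 lost (28%).

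The share stays near a quarter under constant hazard. It would be larger if withdrawals cluster early.

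**How much a test could say, all participants included.** The chance of no placebo withdrawal is 0.9^14 = 0.229 at 10%, 0.8^14 = 0.044 at 20% and 0.7^14 = 0.007 at 30%. If the 10% applies to sirolimus and the hazard ratio is HR, the chance is 0.9^(14/HR): 0.48 at HR 2 and 0.69 at HR 4, with 4.9 and 4.6 expected events.

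Take the most extreme split, all k events on sirolimus, with pᵢ = (42 − i)/(56 − i) for i = 0 to k − 1:

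- Score (log-rank) statistic (k − Σpᵢ)²/Σpᵢ(1 − pᵢ): 1.38 at k = 4 (p = 0.24) and 2.13 at k = 6 (p = 0.14).
- Likelihood-ratio statistic −2Σ ln pᵢ: 2.38 (p = 0.12) and 3.65 (p = 0.056).
- Exact one-sided p, approximated by C(42,k)/C(56,k): 0.30 at k = 4, 0.22 at k = 5 and 0.16 at k = 6.

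At the planned rate none of these tests reaches 0.05 even in the worst case for sirolimus. An interval is still informative: with 0 of 14 on placebo, the exact 95% upper limit for that arm is 1 − 0.025^(1/14) = 23%.

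**The case against.** The strongest reply is that 9.4.4 never invokes 9.3 and that other parts of the plan suggest a wider safety population. Section 8.2 collects adverse events from consent and sends outcomes by arm to the independent medical monitor twice a year. Section 10.1.6 adds monthly review of adverse events and of losses to follow-up. The safety stopping rule in 10.1.2 counts enrolled patients. On this view the gap is an undefined safety set, not a deliberate exclusion, and about 1.5 participants of 56 is a small number.

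Much of that stands. A reader might infer that the plan cannot show early intolerance at all; the documents do not support this. The 9.3 rule selects participants and does not cut data at month 3, so early events in those who stay on drug are still tabulated, and the monitor sees safety data throughout. Nor is the 9.3 set the only one named, since 6.4 names others without a usable definition. Nor do the first 3 months hold all dose adjustment, because 6.1.2 continues it from Visit 7 onwards.

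A reader might also infer that the Cox test will often yield no p-value. Without a placebo withdrawal the hazard ratio has no finite estimate and the Wald test fails, but score and likelihood-ratio p-values still exist, and 9.4.4 does not specify a Wald test. The 23% also depends on carrying the active-arm 10% over to placebo. Replacing Cox by an exact log-rank test would not help, as the p-values above show; that choice is a matter of preference.

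What the reply does not remove is that 9.3 states one rule for analyses without exception, and no other section gives the statistician a different one for the final safety results.

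**Conclusion.** The point holds as a defect in the stated population. Followed as written, 9.3 leaves participants who stop in the first 3 months out of the adverse-event and laboratory tables, the withdrawal counts and curve, and the primary safety outcome. This conflicts with the data collection required in 8.2. Under 10% withdrawal in both arms and constant hazard, about a quarter of withdrawals are affected (1.5 of 5.6). The direction is towards better-looking tolerability if early stopping is related to the drug.

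Two further matters follow. First, 9.4.4 does not say whether withdrawal is from study drug or from the study, although 7.1 separates them; someone who stops drug but stays in follow-up could be counted either way. Second, with 5 to 6 expected events a significance test is a poor headline for tolerability. That rests on the planning rate and weakens if withdrawal reaches 20% to 30%.

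**What to change.** Before unblinding:

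- In 9.3, state that the 3-month rule does not apply to safety. Add a safety set of everyone who took at least one dose, analysed from first dose by treatment received.
- In 8.2 and throughout 9.4.4, name that set as the population.
- In 9.4.4, say whether withdrawal means from study drug or from the study; if both matter, report both.
- In 9.4.4, make the between-arm difference in 48-week cumulative withdrawal, with a 95% CI from a method that copes with no events in one arm, the main tolerability result. Treat any Cox or log-rank p-value as secondary.
- In 6.4, correct the references to sections that do not exist.

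The cost is a few sentences and no new data. Reported tolerability may look slightly less favourable than under the 3-month rule.
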